9.2 Endpoints

9.2.1 Primary

Part A: number of patients with DLTs and AEs.

Part B: best overall response (CR, PR, SD) per RECIST 1.1 and safety (DLT, AEs), duration of overall response, duration of stable disease.

9.2.2 Secondary

Part A: best overall response (CR, PR, SD) per RECIST 1.1 and PK parameters (C_{max} , clearance [CL], volume of distribution [V_{ss}], terminal elimination half-life [$T_{1/2}$], area under the curve [AUC_{0-t}]) of siRNA, duration of overall response, duration of stable disease.

Part B: PK parameters (C_{max} , CL, V_{ss} , $T_{1/2}$, AUC_{0-t} , $AUC_{0-\infty}$) of siRNA.

9.3 Safety

Safety will be assessed by means of physical examination, weight, vital signs, performance status, laboratory evaluations (hematology, biochemistry), ECG, pain assessment and recording of concurrent illness/therapy and AEs. NCI CTCAE version 5.0 will be used to grade all toxicities. All related AEs will be monitored until resolution. Patients will be monitored for safety and concomitant medications throughout the study.

Safety data will be summarized for the safety evaluable population. These data will include AEs and laboratory parameters. AE terms will be coded using the most current version of MedDRA®.

9.4 Efficacy

Response to treatment will be assessed according to RECIST 1.1. The objective evaluation will be performed at baseline and at the end of even numbered cycles for dose levels 1-4 in Part A and at baseline and at the end of every cycle for dose level 5 in Part A and all patients in Part B of the study.

The efficacy endpoints include best overall response (BOR), disease control rate (DCR= rate of SD+PR+CR), duration of response (DOR), duration of CR, and duration of stable disease (SD).

9.4.1 Duration of Overall Response

DOR is measured from the time of CR or PR (whichever is first recorded) until the first date that recurrent or progressive disease is objectively documented. Only patients with a confirmed CR or PR are included in the analysis. For a patient without evidence of PD, DOR will be censored.

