4.5 Duration of Therapy

Upon completion of Cycle 1, in the absence of disease progression or unacceptable toxicity, patients may continue to be treated with NBF-006 at the same dose and schedule until disease progression, death, withdrawal of consent, Investigator decision to remove patient, or intolerable toxicity, whichever occurs first. A patient may continue on study (even if one or more criterion meets Disease Progression per Response Evaluation Criteria in Solid Tumors [RECIST] 1.1) at the Investigator's discretion if deemed that the drug is well-tolerated and that the patient may continue to receive benefit from continuing treatment.

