8.2 Efficacy Assessments

Patients with measurable disease will be assessed at baseline and during the study by standard criteria. For the purpose of this study, patients should be reevaluated at the end of every even numbered cycle in Part A, dose levels 1-4 (0.15 mg/kg, 0.3 mg/kg, 0.6 mg/kg, 1.2 mg/kg), and at the end of every cycle for dose level 5 (1.6 mg/kg) in Part A and for all dose levels tested in Part B patients. In the event objective response (partial response [PR] or complete response [CR]) is noted, changes in tumor measurements must be confirmed by repeat assessments that should be performed at 4 weeks but no later than 5 weeks for patients in dose levels 1-4 in Part A after the criteria for response are first met. Response will be confirmed at 4 weeks or at the next scheduled scan (at Week 6 of the following cycle) for patients in dose level 5 in Part A and all patients in Part B. If a confirmative scan is done after 4 weeks, the next scheduled scan (at Week 6 of the following cycle) may be omitted. For stable disease (SD), follow-up measurements must meet the SD criteria at least 5 weeks after study entry.

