8.2.4.2 Duration of Overall Response

The duration of overall response is measured from the time measurement criteria are met for CR or PR (whichever is first recorded) until the first date that recurrent or progressive disease is objectively documented (taking as reference for PD the smallest measurements recorded since the treatment started).

The duration of overall CR is measured from the time measurement criteria are first met for CR until the first date that recurrent disease is objectively documented.

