8.2.4.3 Duration of Stable Disease

SD is measured from the start of the treatment until the criteria for progression are met, taking as reference the smallest measurements recorded since the treatment started.

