9.4.2 Duration of Stable Disease

Stable Disease is measured from the start of the treatment until the criteria for progression are met, taking as reference the smallest measurements recorded since the treatment started. Duration of stable disease will be analyzed in a similar method as DOR.

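### Duration of response and duration of stable disease censor patients who die without documented progression

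*Protocol*

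**What the plan says.** - **Duration of response.** Section 8.2.4.2 runs it from first CR or PR "until the first date that recurrent or progressive disease is objectively documented". Section 9.4.1 repeats that end point, limits the analysis to confirmed responders, and adds: "For a patient without evidence of PD, DOR will be censored".
- **Duration of stable disease.** Section 8.2.4.3 states: "SD is measured from the start of the treatment until the criteria for progression are met". Section 9.4.2 repeats this and adds: "Duration of stable disease will be analyzed in a similar method as DOR".
- **Progression.** Sections 8.2.3.1 to 8.2.3.3 define it by target-lesion growth, unequivocal non-target progression or new lesions. Death is not part of the definition.
- **Status.** Section 9.2.1 lists "duration of overall response, duration of stable disease" among the Part B primary endpoints. Section 9.2.2 makes both secondary in Part A.
- **Death as a separate outcome.** Section 4.5 continues treatment "until disease progression, death, withdrawal of consent, Investigator decision to remove patient, or intolerable toxicity, whichever occurs first".
- **Scan schedule.** Under section 8.2, "patients should be reevaluated at the end of every even numbered cycle in Part A, dose levels 1-4". Part A level 5 and all of Part B are scanned every 6-week cycle. Section 7.4 schedules a tumor measurement at end of treatment.

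**The concern.** Read together, these sections censor a patient who dies without a progression scan, on both durations. Censoring is harmless only if the censored patient would have had the same future risk of progression as those still followed. In patients whose advanced cancer has failed standard treatment, a death between scans is plausibly related to the disease, so that assumption is doubtful.

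The usual consequence is that durations look longer than they would if death counted as a failure. A reader of a Part B primary endpoint could take a reported median as time alive and progression-free when it is not. The end-of-treatment scan reduces the number of such cases but cannot help a patient who dies before it is done.

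**Working it through.** The protocol gives no event rate, expected median or sample-size figure for these endpoints, so there is no stated number to reproduce. The first step is a reading of the text; the rest is illustration under assumptions.

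**1. Reading.** A patient with stable disease at week 6 who dies at week 10, before the week 12 scan, has met no lesion-based progression criterion. The end event in 9.4.2 has not occurred. The rule in 9.4.1, carried over by 9.4.2, then censors the patient. No other section overrides this.

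**2. Assumptions.** Share of events that are deaths without progression: f = 10%, 20%, 30%. Median with deaths counted: m = 3 months. Hazards are constant after an initial event-free period g. Each endpoint has such a period by construction. A confirmed response needs a second scan at 4 weeks or later. Stable disease needs at least 5 weeks, with a first scan at week 6 (Part A level 5, Part B) or week 12 (Part A levels 1–4).

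**3. Progression seen continuously.** Counting deaths, the median is m. Censoring them leaves a fraction (1 − f) of the hazard, so the median becomes g + (m − g)/(1 − f). For g = 6 weeks (1.38 months) and f = 0.2: 1.38 + 1.62/0.8 = 3.41 months, a ratio of 1.14. Ratios to m:

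| Event-free period g | f = 10% | f = 20% | f = 30% |
|---|---|---|---|
| none (ceiling only) | 1.11 | 1.25 | 1.43 |
| 4 weeks | 1.08 | 1.17 | 1.30 |
| 5 weeks | 1.07 | 1.15 | 1.26 |
| 6 weeks | 1.06 | 1.14 | 1.23 |
| 12 weeks | 1.01 | 1.02 | 1.03 |

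**4. Progression seen only at 6-weekly scans (stable disease, Part A level 5 and Part B).** Simulation of 200,000 patients per setting. All are alive and progression-free at week 6. Progression is dated at the next scan if the patient is alive then; otherwise death is dated when it occurs. Here f is the share of the underlying hazard due to death. The realized share of deaths without documented progression is slightly higher: 11–13%, 22–25% and 32–36%. Kaplan–Meier medians in months, deaths counted vs censored:

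| Underlying median | f = 10% | f = 20% | f = 30% |
|---|---|---|---|
| 3 months | 4.14 vs 4.14 | 3.98 vs 4.14 | 3.56 vs 4.14 |
| 4 months | 4.14 vs 5.52 | 4.14 vs 5.52 | 4.14 vs 5.52 |
| 6 months | 6.90 vs 6.90 | 6.90 vs 8.28 | 6.90 vs 8.28 |

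The shift is zero in two settings, 0.2 and 0.6 months in two, and one scan interval (1.38 months) in five. Censoring at the death date or at the last scheduled scan gave the same medians.

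**5. Small cohorts.** Same model, underlying median 3 months, 4,000 replicates. The median did not change in 87%, 72% and 59% of groups of five (f = 10%, 20%, 30%), or in 75%, 55% and 38% of groups of eight. Otherwise it was longer; it was never shorter when no scan was missed.

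**6. Direction is not guaranteed.** Take five invented patients: progression at 3, 4, 6 and 7 months, and one death at 5. The median is 5 if the death counts and 6 if it is censored at death. It is 4 if the death is censored at a last scan at 2 months.

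**The case against.** The strongest reply has four parts.

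*It is a choice of estimand.* The four definitions agree with each other, and a progression-only duration is a recognized quantity. Counting death turns the stable-disease measure into time to progression or death, which is something else. Section 4.5 concerns treatment and says nothing about analysis. This stands in part: a progression-only measure could be defended if it were declared and deaths without progression were reported beside it. The protocol does neither.

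*Some of it belongs in the SAP.* Censoring dates are commonly settled there, and their absence from the protocol is not held against it. The end event and the censoring of every patient without progression are different. The protocol fixes both, and a SAP that counted death as an event would contradict section 9.4.1.

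*The sizes are assumed.* This is correct. The 11–43% row has no event-free period, which fits neither endpoint, so it is only a ceiling. The five-in-nine count depends on where the assumed median falls between scans: three of the five come from the 4-month median, just before the 18-week scan (4.14 months). At some other assumed medians there is no shift at all, so the count is not a typical effect.

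*Little depends on it.* The analyses are descriptive, and Part B cohorts are 10, 10 and 4. Duration of response uses confirmed responders only, no decision rule is attached, and deaths appear in the safety reporting. All true. This limits the importance of the point but does not justify leaving the rule on a primary endpoint.

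**Conclusion.** The concern holds. As written, death without documented progression is censored for both durations, by a stated rule and not by omission. The effect is usually to lengthen the durations, more plausibly for stable disease than for confirmed responses.

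Its size cannot be found from the protocol. With 10–30% of events being such deaths, a 3-month median and constant hazards, the inflation is about 1–3% for stable disease in Part A levels 1–4. It is about 6–30% where the event-free period is 4–6 weeks. With 6-weekly scans it is anything from nothing to one scan interval, and in cohorts this small the median often would not move. The text is clear; the magnitude is illustrative. The point should be fixed because both durations are Part B primary endpoints and the correction is cheap, but it affects interpretation only.

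**What to change.** In sections 8.2.4.2, 8.2.4.3, 9.4.1 and 9.4.2, end each duration at the first of documented progression or death from any cause. Censor patients who are alive without progression at their last adequate tumor assessment. If a progression-only measure is really intended, say so and report deaths without progression as a competing event.

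The cost is a wording change in four sections. Deaths on study or within 30 days of the last dose are already reported as serious adverse events (section 8.1.2.7), so they need no new data. Reported durations will tend to be slightly shorter, and the stable-disease measure becomes time to progression or death.

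The remedy is partial. No survival follow-up is stated beyond the 30-day visit, so later deaths are not systematically captured and some informative censoring remains; the report should say so.

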9.4.2 Duration of Stable Disease

Stable Disease is measured from the start of the treatment until the criteria for progression are met, taking as reference the smallest measurements recorded since the treatment started. Duration of stable disease will be analyzed in a similar method as DOR.

9.5 Exploratory/Other Studies

Separate reports will be generated for the analysis of ADAs, immune activation biomarkers, GSTP KD, and other biomarker activity.

9.6 Sample Size

This is an exploratory trial and therefore no sample size calculations have been performed. The number of patients in Part A (up to 20) is based on the planned number of dose escalation cohorts required to identify the MTD. The planned number of patients in Part B is approximately 20-24.

10.0 QUALITY CONTROL AND QUALITY ASSURANCE PROCEDURES

10.1 Monitoring of the Study and Regulatory Compliance

The project manager, or designee, will make an initiation site visit to each institution to review the protocol and its requirements with the Investigator(s), inspect the drug storage area, fully inform the Investigator of his/her responsibilities and the procedures for assuring adequate and correct documentation. During the initiation site visit the eCRFs will be

reviewed. Other pertinent study materials will also be reviewed with the Investigator's research staff. During the course of the study, the monitor will make regular site visits in order to review protocol compliance, examine eCRFs and individual subject's medical records and assure that the study is being conducted according to pertinent regulatory requirements. All eCRF entries will be verified with source documentation. The review of medical records will be done in a manner to assure that patient confidentiality is maintained.

10.2 Curricula Vitae and Financial Disclosure of Investigators

All Principal Investigators will be required to provide a current (within 2 years) signed and dated curriculum vitae, a completed FDA Form 1572 and a financial disclosure statement to Theradex Oncology. All Sub-Investigators will be required to provide a current curriculum vitae and a financial disclosure statement to Theradex Oncology.

10.3 Protocol Modifications

No modification of the protocol should be implemented without the prior written approval of the Sponsor or the Sponsor's representative (Theradex Oncology). Any such changes which may affect a patient's treatment or informed consent, especially those increasing potential risks, must receive prior approval by the IRB/IEC. The exception to this is where modifications are necessary to eliminate an immediate hazard to trial subjects, or when the change involves only logistical or administrative aspects of the trial (e.g., change in monitor, change in telephone number). Other administrative revisions which may impact the clinical portion of a study will be duly reported to the IRB/IEC by the Principal Investigator.

10.4 Publication Policy

The publication of the results of the study will be subject to the terms and conditions of the clinical trial agreement between the Sponsor and Investigators. Sponsor approval is required for publication of any data from this trial.

11.0 ETHICAL CONSIDERATIONS

11.1 Informed Consent

The Investigator will obtain written informed consent from each patient, or their authorized representative, participating in the study. The form must be signed, witnessed and dated before any screening assessments are performed. The informed consent form will contain all the Essential Elements of Informed Consent set forth in 21 CFR, Part 50, the European Union Directive 2001/20/EC and its associated Detailed Guidances, European Union GCP Directive 2005/28/EC, the ICH Guideline for GCP, Section 4.8, and the terms of the Declaration of Helsinki (2013). Copies of the signed document should be given to the patient and filed in the Investigator's study file, as well as the patient's medical record if in conformance with the institution's Standard Operating Procedures.

11.2 Institutional Review Board/Independent Ethics Committee

The study will not be initiated without approval of the appropriate IRB/IEC and compliance with all administrative requirements of the governing body of the institution. This protocol, consent procedures, and any amendments must be approved by the IRB/IEC in compliance with current regulations of the FDA and the European Union as applicable and in accordance with ICH/GCPs. A letter of approval will be sent to the Sponsor prior to initiation of the study and when any subsequent modifications are made. The IRB/IEC will be kept informed by the Investigator, Theradex Oncology or the Sponsor, as required by national regulations, as to the progress of the study as well as to any serious and unexpected AEs.

11.3 Patient Privacy

In order to maintain patient confidentiality, all eCRFs, study reports, and communications relating to the study will identify patients by initials and assigned patient numbers; patients should not be identified by name. In accordance with local, national or federal regulations, the Investigator will allow the Sponsor or designee personnel access to all pertinent medical records in order to verify the data gathered on the eCRFs and to audit the data collection process. Regulatory agencies such as the U.S. FDA may also request access to all study records, including source documentation for inspection. Clinical information will not be released without the written permission of the patient as outlined in the patient consent form.

12.0 DATA HANDLING AND RECORD KEEPING

12.1 Data to be Entered Directly in the Electronic Case Report Form

The eCRF will be the source record.

12.2 Recording of Data

Data collected during the study will be entered in the patient's eCRF by the investigational site staff. The staff will keep records of the patient's visit in the files considered as source documents for the site, e.g., hospital chart, research chart. The Investigator will be responsible for the recording of all data on the eCRF and for submitting the data to the Sponsor or their designee in a timely manner. Should any value be significantly different from normal, the Investigator will comment in the appropriate sections provided in the eCRF. The Investigator will provide access to his/her original records to permit a representative from the Sponsor to verify the proper transcription of data.

12.3 Study Records

U.S. Federal laws require that an Investigator maintain all study records for the indication under investigation for two years following the date a Product Licensing Application is approved or, if no application is to be filed or if the application is not approved for such indication, until two years after the investigation is discontinued and the FDA is notified.

APPENDIX I – ECOG Performance Status

Grade	
0	Fully active, able to carry on all pre-disease performance without restriction.
1	Restricted in physically strenuous activity but ambulatory and able to carry out work of a light or sedentary nature, e.g., light house work, office work.
2	Ambulatory and capable of all self-care but unable to carry out any work activities. Up and about more than 50% of waking hours.
3	Capable of only limited self-care, confined to bed or chair more than 50% of waking hours.
4	Completely disabled. Cannot carry on any self-care. Totally confined to bed or chair.
5	Dead.

APPENDIX II – Common Terminology Criteria for Adverse Events (CTCAE) v5.0

Available from the Cancer Therapy Evaluation Program website:
https://ctep.cancer.gov/protocolDevelopment/electronic_applications/ctc.htm

APPENDIX III – Acceptable Contraceptive Methods

 • Male or female condom with or without spermicide • Cervical cap, diaphragm, or sponge with spermicide

Highly Effective Contraceptive Methods That Are User Dependent ^a Failure rate of <1% per year when used consistently and correctly.

 • Combined (estrogen- and progesterone-containing) hormonal contraception ^b 
 ○ Oral ○ Intravaginal ○ Transdermal ○ Injectable

 • Progestogen-only hormonal contraception ^b 
 ○ Oral ○ Injectable

Highly Effective Methods That Have Low User Dependency Failure rate of <1% per year when used consistently and correctly.

 • Progesterone-only contraceptive implant ^{b, c} • Intrauterine hormone-releasing system (IUS) ^b • Intrauterine device (IUD) • Bilateral tubal occlusion

 • Vasectomy 
Vasectomy is a highly effective contraception method provided that the partner is the sole male sexual partner of the female of childbearing potential and the absence of sperm has been confirmed. If not, an additional highly effective method of contraception should be used.

 • Sexual abstinence 
Sexual abstinence is considered a highly effective method only if defined as refraining from heterosexual intercourse during the entire period of risk associated with the study treatment. The reliability of sexual abstinence needs to be evaluated in relation to the duration of the study and the preferred and usual lifestyle of the participant.)

Notes:
 
Use should be consistent with local regulations regarding the use of contraceptive methods for participants of clinical studies.
 
a) Typical use failure rates are lower than perfect-use failure rates (i.e., when used consistently and correctly).
 
b) If hormonal contraception efficacy is potentially decreased due to interaction with study treatment, condoms must be used in addition to the hormonal contraception during the treatment period and for at least 120 days, (corresponding to time needed to

eliminate study treatment plus 30 days for study treatments with genotoxic potential) after the last dose of the study treatment.

c) If locally required, in accordance with Clinical Trial Facilitation Group (CTFG) guidelines, acceptable hormonal contraceptives are limited to those which inhibit ovulation.
